# MSSM Protocol Template HRP-503a

## Brief Summary of Research (250-400 words):

Anorexia nervosa (AN), a characteristically relentless pursuit of thinness with an intense fear of weight gain despite significantly low body weight, is a serious psychiatric disorder with high rates of morbidity and mortality. Low weight eating disorders (LW-ED), the broader category of eating pathology that includes AN and similar variants, are characterized by a chronic course, poor response to treatment, and food avoidance. Emerging neuroimaging evidence suggests that deficits in insula-amygdala-ventral striatum (IAVS) neurocircuitry contribute to individual variability in aversive and reward learning, and that these brain regions demonstrate abnormal responses to food/eating stimuli. Our pilot data suggest that patients with LW-ED experience difficulty extinguishing food-cue associations in a reversal learning paradigm compared to healthy controls, a difficulty that is related to psychophysiological measures of aversive disgust (not fear). We have also successfully piloted an interoceptive exposure intervention for this population that targets visceral sensitivity and seeks to increase 'top-down' regulation of the IAVS neurocircuit. The proposed project will (a) use novel fMRI-EMG to test the relationship between effective connectivity within amygdala-insula-ventral striatum network and its relationship to psychophysiological and behavioral measures of acute threat and reward learning in 60 adolescents with LWEDs and 30 healthy controls, (b) test the sensitivity of this network to an experimental interoceptive exposure paradigm relative to patients receiving family based therapy for weight restoration using dynamic causal modeling of fMRI-EMG data pre-post experimental conditions, (c) validate this model against objective measures of laboratory and real world eating behavior. The results of this study will help us better understand the core neurocircuitry that underlies both threat processing and reward/aversive learning and how this circuit relates to objective behavior. Further, we will determine the modifiability of this neurocircuitry via two distinct behavioral interventions chosen to target different aspects of affective processing and reward learning. These data will be used to inform future clinical interventions targeting aversive/reward learning within this population and dysregulation in insulaamygdala-ventral striatum subcircuits.

# 1) Objectives:

Protocol Title:	Reward Systems and Food Avoidance in Adolescents with	
	Low Weight Eating Disorders	
Principal Investigator	[name]	
Name/Contact Info:	[contact]; [contact]	
Primary Contact	[name]	
Name/Contact Info	[contact]; [contact]	
Date Revised:		
Study Number:	GCO#15-0939 IF# 2446156 HS# 16-00570	

Our primary objectives are to test our disgust-conditioning model of food avoidance adolescent patients with low-weight eating disorders. We aim to do this by investigating the underlying neurocircuitry involved in food-cue learning and its reversal (i.e., updated learning through reversal of cue-absence vs. cue-target). Our aims are:

- Aim 1: Delineate neurocircuitry through which aversive-disgust responses to palatable food hijack the *acquisition* of food-cue associations in adolescents with LW-EDs versus health controls.
- Aim 2: Characterize the impairments in neurocircuitry that underlies resistance to food-cue *extinction* in adolescents with LW-EDs versus controls.
- Aim 3: Determine the effect of 6-sessions of interoceptive-exposure (IE) and family based therapy for weight regain on neurocircuitry for aversive food-cue *acquisition* and *exposure* in adolescents with LW-EDs.
- Aim 4: Assess the relationship between eating behavior and neurocircuitry for food-cue acquisition and extinction at baseline and following intervention.

#### **Research Question:**

We have two primary research questions to be investigated in this proposal. First, we are testing for group differences in the underlying neurocircuitry of aversive learning among adolescents with low weight eating disorders and healthy controls and validating this neurocircuitry across multiple domains (psychophysiology of emotion, symptom expression, and objective and real world eating behavior). Our second primary research question is whether interoceptive exposure can modify the connectivity within the neuronetwork that underlies food-cue learning in patients with low-weight eating disorders. We will validate these changes through psychophysiology measures of emotion, symptom change, and measures of objective and real-world eating behavior.

#### The proposed project will

- (a) use novel fMRI-EMG to test the relationship between effective connectivity within amygdala-insula-ventral striatum network and its relationship to psychophysiological and behavioral measures of acute threat and reward learning in 60 adolescents with LW-EDs and 30 healthy controls.
- (b) test the sensitivity of this network to an experimental interoceptive exposure paradigm relative to patients receiving family based therapy for weight restoration using dynamic causal modeling of fMRI-EMG data pre-post experimental conditions. IE, a behavioral intervention hypothesized to work via altering prefrontal regulation of the insula response to aversive stimuli by decreasing visceral sensitivity, will be compared to a contingency

M
////
Mount
Sinai

Protocol Title:	Reward Systems and Food Avoidance in Adolescents with	
	Low Weight Eating Disorders	
Principal Investigator	[name]	
Name/Contact Info:	[contact]; [contact]	
Primary Contact	[name]	
Name/Contact Info	[contact]; [contact]	
Date Revised:		
Study Number:	GCO#15-0939 IF# 2446156 HS# 16-00570	

management driven family-based weight gain control (FB-WGC) intervention hypothesized to modify the striatal response to food by changing incentive value of food.

(c) validate this model against objective measures of laboratory and real world eating behavior.

# 2) Background

### **Low-Weight Eating Disorders**

Significance of Low Weight Eating Disorders and the IAVS Sub-Network. Anorexia nervosa (AN) is a serious psychiatric disorder with high rates of morbidity and mortality(1-6). To date, DSM-variants of AN are most commonly examined in research studies; however, the characteristic features of this disorder remain unchanged regardless of nosological system, namely a relentless pursuit of thinness with an intense fear of weight gain despite significantly low body weight(7). In this broader dimension of low weight eating disorder (LW-ED), we posit that food-cue learning relies on an interconnected network of the insula, anterior cingulate cortex, amygdala, and ventral striatum. This IAVS sub-network assigns valence and feeds forward salient sensory information to prefrontal regions involved in decision making and choice, and contains key nodes known to be dysregulated among LW-ED adolescents(8). IE, a behavioral intervention that theoretically targets the IAVS sub-network to extinguish learned associations characterized by visceral sensitivity, offers the best test of this theory. Studying a model of impaired food-cue (i.e., stimulus-response) learning and affective processing in LW-ED will help advance recent theories of impaired habit formation(7) and emotion regulation(9) in AN, and is a natural extension of our clinical expertise with LW-ED(10) and experience developing exposure therapies with this population(11).

#### **Reversal Learning and Low Weight Eating Disorders**

Figure 1. Summary of Conditioned Safety and Aversion to Food

A) Cued Safety

Environmental Input

B)Cued Aversion

CS+

Vironmental Input: Somatic, neutral, and food (or its absence) co-occur. Acquisition: peated co-occurence leads to emotional salience directed by interoceptive input related to

Figure 1 highlights the basic conditioning processes we theorize cause persistent food avoidance among patients with LW-ED. Aversive conditioning and extinction models are broadly implicated in mental illness(12) and have a well-

defined neurocircuitry translated from pre-clinical

A.1.1 Reversal Learning

and Food Avoidance.

peated co-occurence leads to emotional salience directed by interoceptive input related to od (e.g., bloating) or food absence (e.g., empty stomach). Conditioned Response: Emotional response influences behavioral decisions about food and its avoidance.

response influences behavioral decisions about food and its avoidance. Effective Date: 4/12/2022

End Date: 4/11/2023

Protocol Title:	Reward Systems and Food Avoidance in Adolescents with
	Low Weight Eating Disorders
Principal Investigator	[name]
Name/Contact Info:	[contact]; [contact]
Primary Contact	[name]
Name/Contact Info	[contact]; [contact]
Date Revised:	
Study Number:	GCO#15-0939 IF# 2446156 HS# 16-00570

to human studies(13-15). Our theory builds on seminal work by Co-I [name](16), which extends classic conditioning models to reversal learning. The latter offers a measure of the ability to extinguish learned associations in the context where the original threat remains present in the environment, despite the extinction of the conditioned stimulus (CS)+UCS association. Consequently, reversal learning may better generalize to human experience where the predictability of threat changes, but the threat remains(17). Among patients with LW-EDs, impaired reversal of food associations could be why dieting (i.e., associations of calorie dense food with an aversive threat state) becomes a chronic, pathological pattern of food avoidance. In our model (see **Figure 1**), stimuli that signal information about food (e.g., eating environments) and eating itself become associated with an aversive state (i.e., feeling fat, gross, etc.) and other stimuli (e.g., dieting tips, exercise cues, etc.) are paired with 'safety' or the absence of this aversive state (e.g., empty stomach). These relationships form in the context of a typical diet and motivate food avoidance, resulting in weight loss. However, when weight loss becomes unhealthy, it should be possible to reverse these associations to promote consumption of higher density food and avoid the reversed cue associated with the threat of malnutrition. Individuals with LW-ED fail to reverse these associations, which contributes to food avoidance.

## Development of Interoceptive Exposure for Food Avoidance and Visceral Sensitivity

Our interoceptive exposure (IE) was developed to reduce visceral sensitivity by altering interoceptive conditioning similar to interventions for irritable bowl syndrome(18-22), consequently increasing tolerance for insula-driven interoception. IE specifically reduces the threshold for visceral sensitivity in anxiety(22, 23) and somatic disorders(24). IE mediates psychotherapy outcomes via specific reductions in visceral sensitivity(25-27) indicating that IE works by changing the influence of interoceptive information on affect and associated behavior (e.g., avoidance). We have developed and pilot tested a 6-Session IE module for LW-ED(11, 28). Details regarding the IE intervention are provided in multiple other sections of the application. Visceral sensitivity plays a primary role in food choice and consumption, and increased tolerance of these sensations should reduce the use of food avoidance. As the insula is integral to almost all salient aspects of food/eating, including somatic symptoms (e.g., stomach distention in the absence of food(29)), we theorize IE targets the effective role of the insula in processing food-cue associations characterized by visceral sensitivity (e.g., bloating, etc.).

#### Eating and AN

Although some research has attempted to measure the pathology of eating behavior, most of the measures are subjective and rely heavily on patient report. Currently, there is a limited amount of studies that have objectively examined the food intake of patients

Protocol Title:	Reward Systems and Food Avoidance in Adolescents with	
	Low Weight Eating Disorders	
Principal Investigator	[name]	
Name/Contact Info:	[contact]; [contact]	
Primary Contact	[name]	
Name/Contact Info	[contact]; [contact]	
Date Revised:		
Study Number:	GCO#15-0939 IF# 2446156 HS# 16-00570	

with low weight eating disorders. An examination of the eating behavior among adult women with anorexia nervosa in an inpatient setting showed that despite improvements in psychological symptoms, eating disturbances persisted after patients achieved weight restoration(30). The level of anxiety is modifiable via traditional exposure therapy(31, 32), however, these changes have almost no measurable impact on eating behavior. Consequently, adaptations to interventions that may improve eating behavior have significant value in developing treatments for this population.

## 3) Setting of the Human Research

Research will take place at the Mount Sinai Eating and Weight Disorders Program (EWDP) (for consenting, intakes, and behavioral/psychological assessment) and Translational and Molecular Imaging Institute (TMII) at the Icahn School of Medicine at Mount Sinai to conduct fMRI tasks and EMG readings.

Potential subjects will be identified through our clinic, and through other referrals from their treatment providers, as well as through flyers distributed throughout Mount Sinai and the surrounding areas. As per Mount Sinai Resource, we will be also recruiting via MSSM Update Weekly Newsletter, MSSM psychiatry list-serv and MSSM post-doc list-serv.

## 4) Resources Available to Conduct the Human Research

The Mount Sinai EDWP sees a high volume of clients, many of whom fall within the age and eligibility guidelines for this study. Therefore, we expect no difficulty recruiting all participants within the planned time schedule.

Prior to commencing this study, all persons assisting with this research will be trained on the protocol instructions detailing their trial-related duties and functions will be provided in a clear and concise manner. In addition, all persons assisting with this research will have completed the IRB education requirements for Human Subjects research prior to their involvement in the study.

#### **Principal Investigator:**

The PI will be responsible for monitoring and directing the overall progress of all aspects of the study proposed in this application. Specifically, the PI will screen potential research participants, oversee training of the research assistants, supervise database creation and entry, and serve as the secondary statistician on data analyses (ensuring data quality, management, and interpretation of statistical models). He will also lead weekly staff meetings and be responsible for submitting grant related materials (IRB, Progress

Protocol Title:	Reward Systems and Food Avoidance in Adolescents with	
	Low Weight Eating Disorders	
Principal Investigator	[name]	
Name/Contact Info:	[contact]; [contact]	
Primary Contact	[name]	
Name/Contact Info	[contact]; [contact]	
Date Revised:		
Study Number:	GCO#15-0939 IF# 2446156 HS# 16-00570	

Report, etc.) and lead efforts in manuscript preparation and publication from the study. Further, the PI will be one of the providers of the experimental 6-week behavioral challenge.

### **Co-Investigators**:

Co-Investigators will be responsible for reviewing data collected during the single and multi-item test meals (e.g., amount and types of food consumed) and will assure the quality of the laboratory meal assessments. They will work closely to offer expertise related to the measurement of eating behavior and assist with the interpretation of data, the presentation of results, and preparation of study reports. The Co-Investigators will examine scans to check for medical abnormalities, aid in the interpretation of neurobiological data and results overall, and review labs for medical clearance to participate in the study. Additionally, Co-I's will aid in the collection and analysis of EMG data, oversee the data processing and the statistical analysis of imaging data. They will also be responsible for ensuring the integrity of the scans and behavioral data collected from the reversal learning task.

Co-I's will also contribute to data analysis by co-registering the facial EMG findings with the neuroimaging data and using dynamic causal modeling to examine connectivity within the regions of interest.

Another Co-I role will be analyzing data obtained from the FaceReader emotional detection software. FaceReader output is of a high density, with 20 recordings made every second. Furthermore, many of the recordings will be obtained while the participant is eating, adding to the amount of noise present in the data (i.e., the act of chewing can be mistaken for emotional reactions). The Co-I will oversee the data processing and analysis of these data after data has been collected, fitting the best models while removing as many of the extraneous recordings as possible. They will work closely to estimate and calibrate DCMs and advise on issues related to data interpretation.

#### **Non-Key Personnel:**

#### Clinical Psychologist

The Clinical Psychologist will be primarily responsible for diagnostic interviewing and for providing the behavioral challenge. They will oversee coordination between the post-doctoral fellow and research assistant to generate integrity ratings for interviews and will have immediate oversight of the clinical status of participants with low weight eating disorders.

#### Nutritionist

The nutritionist will aid the Co-I in the preparation and coding of the test-meal replacement shake and standardized multi-item meal. Specifically, the nutritionist will assist with the execution and analysis of laboratory test meals (e.g., measuring food residue), and will help with the interpretation of eating behavior data.

Protocol Title:	Reward Systems and Food Avoidance in Adolescents with	
	Low Weight Eating Disorders	
Principal Investigator	[name]	
Name/Contact Info:	[contact]; [contact]	
Primary Contact	[name]	
Name/Contact Info	[contact]; [contact]	
Date Revised:		
Study Number:	GCO#15-0939 IF# 2446156 HS# 16-00570	

#### Post-Doctoral Fellow

The post-doctoral fellow will be responsible for diagnostic interviewing and for providing the behavioral challenge. The post-doctoral fellow will also coordinate with the research assistant to generate integrity ratings for interviews and will have immediate oversight of the study's process.

### Clinic Research Coordinators

Our coordinators will work closely with the PI, and will attend to the administrative components of the project. These responsibilities include, but are not limited to, recruitment of subjects; coordinating and scheduling clinical assessments; ensuring that all rating scales and clinical reports are completed in a timely fashion; ensuring that checks are generated to reimburse subjects for their participation in the protocol as well as other fiscal aspects of the study (e.g., purchasing supplies). In addition, this person will be responsible for preparing all IRB documentation and will make sure that all consenting of subjects is appropriately completed.

#### Volunteers

Our volunteer interns will work closely with the PI and the Clinical Research Coordinators on this project. Responsibilities include, but are not limited to, recruitment of subjects, escorting participants to other areas at Mount Sinai and inputting data.

# 5) Study Design

# a) Recruitment Methods

Adolescent female participants with AN and healthy comparison controls will be recruited for this study. Participants will be recruited via phone calls to the Project Coordinator at the Mount Sinai Eating and Weight Disorders Program, and through advertisements and emails to listservs of school counseling centers, and hospitals. In addition, the study will be publicized on the Mount Sinai Clinical Trials and Eating and Weight Disorders Program websites, as well as in the local media via IRB-approved flyers. Staff will recruit healthy comparison controls predominantly through posting flyers at local schools and community centers. All potential advertising tools will be submitted to the IRB for approval prior to their use. Participants will be instructed to contact the Project Coordinator at [contact] and will be invited for a consultation in which the study will be thoroughly explained to them in verbal and written form by the principal investigator or by another member of the research team (i.e. project coordinator, research assistant, or extern therapists). Individuals that call the Mount Sinai Eating and Weight Disorder Program looking for treatment will be informed of the study. Interested participants and/or parent(s) will be informed that at

Reward Systems and Food Avoidance in Adolescents with	
Low Weight Eating Disorders	
[name]	
[contact]; [contact]	
[name]	
[contact]; [contact]	
GCO#15-0939 IF# 2446156 HS# 16-00570	

least one parent or legal guardian will be expected to attend the initial in-person screening visit with the adolescent participants and provide informed consent at that time.

## b) Inclusion and Exclusion Criteria

### **Low Weight ED Patients**

#### *Inclusion criteria:*

- Females,
- Adolescents ages 12-18,
- Speak English,
- Seeking treatment
- Refusal to maintain greater than minimally low body weight based on BMI for age percentiles and growth trajectories,
- Clinically significant restriction of food intake on the dietary restraint subscale
  of the EDE or evidence of persistent food avoidance as reported by patient or
  guardians.
- Given medical clearance from pediatrician or equivalent.

#### Exclusion criteria:

- Current psychotropic medication that would have an effect on performance on behavioral tasks (i.e., anti-anxiety medication),
- Comorbid psychotic or bipolar disorder,
- Active suicidal ideation,
- Major medical illness known to influence eating or weight,
- Current substance dependence,
- Previous exposure therapy for LW-ED.
- Physical limitation that would prevent participation (e.g., allergic to chocolate),
- For patients with current or a history of sexual or physical abuse by parents, siblings, or guardians, perpetrators of the abuse will be excluded from treatment; if physical or sexual abuse by a family member occurs during the course of treatment, perpetrators will be excluded from ongoing treatment

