## c) Number of Subjects

A total of 118 female adolescents will be recruited to obtain complete assessments on 60 female adolescents with a low weight ED and 30 healthy comparison adolescents between the ages of 12-18.

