#### Assessments:

- EDA-5 for eating disorder diagnoses and psychopathology.
- Relevant sections of the *K-SADS* (mania, psychosis, alcohol and substance abuse) to determine any lifetime psychiatric disorder to determine eligibility.
- Columbia-Suicide Severity Rating Scale (C-SSRS) to assess for suicidal ideation.

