### **Treatment (Visits 3-8)**

After the baseline assessment (Visits 1-2), patients with LW-EDs will be randomized to 6 weekly sessions of FBT-WG or IE. Randomization will occur after we have processed the baseline fMRI scans. If the study coordinators have determined the participant's scan is free of interference from motion in the scanner, the participant will be randomized within this group. If the study coordinators determine a participant's scan is unusable, the participant will be excluded from the study.

In both FBT-WG and IE, the first session lasts two hours and the remaining 5 sessions last one hour.

FBT-Weight Gain Control (FBT-WG): Participants and families randomized to FBT-WG will receive 6-weeks of FBT treatment for AN. Sessions occur weekly, with the first session lasting two hours and the remaining 5 sessions one hour. FBT is atheoretical in terms of the etiology, but uses parent-enforced contingencies to increase value of eating and decrease the value of food avoidance. The six sessions of FBT focus primarily on disordered eating, using a functional analysis to facilitate parental use of positive/negative contingencies to motivate eating behavior. In session 2, a family meal provides the therapist with an opportunity for direct observation of the familial interaction patterns around eating. The therapist makes careful and persistent requests for united parental action toward re-feeding and/or regulating eating habits, the primary concern at this point of the treatment, and the therapist tries to create and reinforce a strong parental alliance around efforts at feeding the child, and align the patient with the sibling sub-system. Parents are taught to reinforce even minimal efforts at eating and creating clear consequences for food avoidance and successful eating. Weekly sessions offer an opportunity for therapist to reinforce/update the contingency plan and reinforce the parents for remaining consistent and persistent in their re-feeding of the adolescent.

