tolerate their interoceptive experience (e.g., disgust), so that eating can become more flexible. At the end of the first session, the therapist and parent(s) review a manual, which provides clear instructions for structuring the re-feeding process (e.g., sitting with child during all mealtimes; guidelines for IE homework; planning meals). In the 2nd hour, participants are given a meal replacement shake and instructed to focus on internal bodily sensations and to continue eating while experiencing and labeling these sensations. This practice is then assigned for homework, charging parents with orchestrating IE in similar pattern using a visceral sensitivity hierarchy established in the first session and is continued through the end of the module. The therapist uses an empathetic active stance to encourage IE that will subsequently serve as an example for parents in IE homework assignments. Participants rate their level of distress 4 times in the session and physiological response is recorded using EMG and facial recognition software. The remaining 5 sessions last one hour, and participants eat a meal replacement shake over 30-minutes, identical to the first session. All sessions include debriefing and development of IE homework that includes daily practice of IE.

Visit 9 and 10: These visits will follow the same procedures as Visits 1 and 2 respectively.

The eating sessions in visits 1 and 2 and visits 3 and 4 (9 and 10 for adolescents with a low weight eating disorder) and the treatment sessions (visits 3-8) will be video recorded to be decoded via software to analyze participants' emotional responses to eating. Treatment integrity will also be evaluated from the recording of the intervention sessions. The video recordings will be stored securely for the duration of the study in a password protected file that only the study staff can access.

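### Does excluding prior exposure therapy, but not prior FBT, tilt the IE versus FBT-WG comparison?

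*Protocol*

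**What the plan says.** Section 5b of the Protocol requires LW-ED patients to be "Seeking treatment" and excludes those with "Previous exposure therapy for LW-ED". Neither list mentions prior FBT or any other family therapy.

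Under Treatment (Visits 3-8) in section 5f, the comparator is FBT: "Participants and families randomized to FBT-WG will receive 6-weeks of FBT treatment for AN". On the timing of allocation the same section says "Randomization will occur after we have processed the baseline fMRI scans". It makes a usable scan a condition of allocation and names no stratification factor.

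The Visit 1 eating-disorder interview is described as "EDA-5 for eating disorder diagnoses and psychopathology". The other listed items are four K-SADS sections, the C-SSRS, six self-report scales, medical clearance, the shake meal, and height and weight. Treatment history is not among them.

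Section 3 gives the source of patients: "Potential subjects will be identified through our clinic, and through other referrals from their treatment providers". Section 5c plans "to obtain complete assessments on 60 female adolescents with a low weight ED".

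**The concern.** The only exclusion on earlier psychotherapy protects one arm. Patients come partly from an eating-disorder clinic and from treating providers, so some may already have had FBT. Those still ill could be allocated to more of it, whereas no one in the IE arm can have failed exposure before.

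If earlier FBT weakens the response to FBT-WG more than the response to IE, part of any IE advantage under Aim 3 or Aim 4 would reflect who was enrolled. The Protocol also does not say that prior FBT is recorded. If it is not, no analysis could later examine the question, whatever a SAP provides.

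**Working it through.** **What the text fixes.** The asymmetry is real: one prior treatment is excluded and the other is not mentioned. The Protocol states no share with prior FBT, effect size, SD or allocation ratio, so there is no figure of its own to reproduce. What follows is an illustration on assumed inputs.

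**Inputs.** 60 LW-ED completers (section 5c), and an assumed 1:1 split, giving 30 per arm. Assumed: p = share with prior FBT; d = effect in first-time patients, in SD; L_FBT and L_IE = fraction of that effect lost in pretreated patients in each arm.

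**Standard error of the contrast.** sqrt(2/30) = 0.258 SD.

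**Gap between the enrolled and the FBT-naive contrast**, assuming the arms are equal in naive patients: shift = p × d × (L_FBT − L_IE). The chance of a significant result favouring IE is 1 − Φ(1.96 − shift/0.258).

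| Case | Shift | Chance |
|---|---|---|
| Mild: p 10%, d 0.5, L_FBT 0.5, L_IE 0 | 0.1 × 0.5 × 0.5 = 0.025 SD | 3.1% |
| Mild, IE loses half as much | 0.1 × 0.5 × 0.25 = 0.0125 SD | 2.8% |
| Extreme: p 40%, d 1.0, L_FBT 1, L_IE 0 | 0.4 × 1 × 1 = 0.40 SD | 34% |
| Extreme, IE loses half as much | 0.4 × 1 × 0.5 = 0.20 SD | 12% |
| Both arms lose the same | 0 | 2.5% |

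**What these percentages mean.** They are not false-positive rates for the trial's comparison. If prior FBT does weaken FBT-WG in some enrolled patients, the average difference between the arms in that population is real, and the last column is the chance of detecting it. It would mislead only a reader who applied it to FBT-naive patients.

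**Is L_IE = 0 plausible?** The IE arm also contains parent-led re-feeding. Its parents are given written guidance, described thus: "which provides clear instructions for structuring the re-feeding process (e.g., sitting with child during all mealtimes; guidelines for IE homework; planning meals". Earlier FBT may therefore blunt both arms, which moves the cases towards the bottom row.

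**Chance imbalance.** With 30 per arm and no stratification, the arms differ by five or more pretreated patients with probability about 5% (p = 10%), 18% (p = 25%) or 25% (p = 50%). Imbalance of this kind is part of what the standard error of a randomised contrast already allows for.

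**Would an FBT-naive analysis help?** The naive group is nested in the full sample, so with m naive patients per arm SE(naive − overall) = sqrt(2/m − 2/30).

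- 40% pretreated, m = 18: sqrt(0.1111 − 0.0667) = 0.21 SD; half-width 1.96 × 0.21 ≈ 0.41 SD, against a largest shift of 0.40 SD.
- 20% pretreated, m = 24: sqrt(0.0833 − 0.0667) = 0.13 SD; half-width ≈ 0.25 SD, against a largest shift of 0.2 × 1 × 1 = 0.20 SD.

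In both cases the check is too imprecise to show even the worst shift reliably.

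**The case for a change.** The strongest case for a change is that balance in expectation does not remove effect modification. Section 1 gives the two arms different mechanisms: IE acts on prefrontal regulation of the insula response, and FBT on the striatal response to food. Prior FBT need not blunt both equally. Moreover, a SAP cannot adjust for a variable that was never collected, and one screening question costs almost nothing.

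The point about effect modification stands, but it limits generalisability and does not bias the randomised contrast. Its size and direction are unknown. Nothing in the Protocol links earlier FBT to a smaller change in connectivity, which is the subject of Aim 3. The link is more plausible for eating behaviour under Aim 4, but it cannot be quantified there either.

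The point about collection rests on silence. The Visit 1 list is not exhaustive: the data management section says demographic information is stored, yet no demographic item is listed for Visit 1. The exclusions for prior exposure therapy and for abuse history likewise need questions that are not listed. Staff must ask about past treatment to apply section 5b, so prior FBT may well come up at the same time. What can be said is that the Protocol does not state that it is recorded.

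**Conclusion.** The asymmetry is in the text, but the plan still gives a sound comparison for the patients it enrols. The remaining limit is generalisability to FBT-naive patients. On assumed inputs this runs from 0 to 0.40 SD. The upper end needs 40% pretreated, a 1.0 SD effect, complete loss in FBT-WG and none in IE; the mild cases are 0.0125 to 0.025 SD. All of this assumes 30 completers per arm.

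The exclusion criterion need not change. The numbers do not support a stratum, or a decision rule based on an FBT-naive subgroup, because such an analysis could not reliably show even the extreme shift. The investigators may choose to note prior FBT when they ask about prior exposure, describe it by arm, and say that the sample may include previously treated patients. That is ordinary descriptive reporting, and the validity of the result does not depend on it.
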